## **6.9. Treatment after the End of the Study**

The Investigator is responsible for ensuring that consideration has been given to the post-study care of the subject's medical condition, whether or not GSK is providing specific post-study treatment.

Subjects will not receive any additional treatment from GSK after completion of the study because the 12 week duration of treatment is limited by the supporting 13 week toxicology studies.

## **6.10. Lifestyle and/or Dietary Restrictions**

- Subjects must adhere to the contraceptive requirements listed in [Appendix 6](#).

### **6.10.1. Activity**

- Subjects will abstain from strenuous exercise more than their normal routine for 48 hours prior to each blood collection for clinical laboratory tests.
- Subjects who have consented to synovial biopsies will abstain from strenuous exercise for 24 hours after synovial biopsy procedures.

## **6.11. Concomitant Medications and Non-Drug Therapies**

### **6.11.1. Permitted Medications and Non-Drug Therapies**

Selected medications for the treatment of RA may be taken, with specific requirements listed in [Table 1](#), and as long as they are not prohibited (Section [6.11.2](#)). All concomitant medications taken during the study will be recorded in the source document and CRF. The minimum requirement is that drug name and dates of administration are recorded.

**Table 1 Specific Requirements for Permitted Medications During the Study**

Drug	Requirement
Methotrexate	Stable dose regimen (up to 25 mg/week) for at least 12 weeks prior to screening and remain on this dose throughout the study (unless dose must be reduced because of a safety concern). MTX should ideally be taken on the same day of week and at approximately the same time of day throughout the study.
Sulfasalazine	Stable dose regimen for at least 12 weeks prior to screening and throughout the study.
Hydroxychloroquine or chloroquine	Stable dose for at least 12 weeks prior to screening and throughout the study.
Leflunomide	Stable dose for at least 12 weeks prior to screening and throughout the study.
Folate supplements (minimum of 5 mg/week)	If a subject is on folate supplements with MTX treatment, they must be on a stable dose regimen for at least 4 weeks prior to randomization and throughout the study.
Other oral anti-rheumatic therapies such as non-steroidal anti-inflammatory drugs (NSAIDs), oral glucocorticoids (e.g., prednisolone $\leq$ 10 mg /day. See Appendix 3 for equivalent doses).	Stable dose regimen for at least 4 weeks prior to screening and throughout the study (unless reduction required due to adverse effects). Omit dose on the morning prior to study visits until after joint assessments.

### 6.11.2. Prohibited Medications and Non-Drug Therapies

[Table 2](#) lists prohibited medications for defined periods of time before and during the study until after the follow up visit.

Subjects who start prohibited medications or therapies as a treatment for RA or other reasons during the study will be withdrawn from study treatment for safety reasons. If in any doubt, Investigators are advised to discuss medications with the medical monitor.

**Table 2 Prohibited Medications**

Therapy	Time period
A change in dose of methotrexate or other DMARD.	12 weeks prior to screening until after the follow up visit (Day 112)
Greater than 10mg/day oral prednisolone (or equivalent glucocorticoid) or a change in dose of corticosteroid.	4 weeks prior to screening until after the follow up visit (Day 112)
Intramuscular glucocorticoids (e.g., methylprednisolone ≤120 mg/month)	4 weeks prior to screening until after the follow up visit (Day 112)
Intra-articular corticosteroid injections	6 weeks prior to screening and until after the follow up visit (Day 112).
Janus Kinase (JAK) Inhibitors	4 weeks prior to screening until after the follow up visit (Day 112).
P-glycoprotein (Pgp) inhibitors including but not limited to amiodarone, azithromycin, captopril, carvedilol, clarithromycin, conivaptan, cyclosporine, diltiazem, dronedarone, erythromycin, felodipine, itraconazole, ketoconazole, lopinavir, ritonavir, quercetin, quinidine, ranolazine, ticagrelor, verapamil [FDA, 2012].	4 weeks prior to first dose (Day 1) until after the follow up visit (Day 112).
Narrow therapeutic index (NTI) CYP3A4 substrates including but not limited to alfentanil, astemizole, cisapride, cyclosporine, dihydroergotamine, ergotamine, fentanyl, pimozone, quinidine, sirolimus, tacrolimus, terfenadine [FDA, 2012].	4 weeks prior to the first dose (Day 1) until after the follow up visit (Day 112).
Biologic therapies for the treatment of rheumatoid arthritis not limited to anti-TNF biologics or other biologics, rituximab, anakinra, abatacept or tocilizumab.	At any time.

Exposure to more than one anti-TNF biologic therapies for the treatment of RA including but not limited to anti-TNF biologics, infliximab, adalimumab, etanercept, certolizumab and golimumab.
 
Exception: Exposure to a single anti-TNF-biologic for which the subject discontinued for a reason other than primary non-response is permitted.
	
Cannot have been exposed to more than one anti-TNF biologic or be on at any time during the study.
 
In the case of a single anti-TNF biologic for which the subject discontinued for a reason other than primary non-response, the subject must not be on for 8 weeks or 5 half lives (whichever is longer) prior to first dose until after the follow up visit (Day 112).

Live vaccination	Live or attenuated vaccinations are not permitted within 30 days of randomization or plan to receive a vaccination during the study until follow-up visit. If indicated, non-live vaccines (e.g., inactivated influenza vaccines) may

Therapy	Time period
	be administered whilst receiving GSK2982772 based on an assessment of the benefit:risk (e.g., risk of decreased responsiveness). Investigators are expected to follow local and/or national guidelines with respect to vaccinations, including against pneumococcus and influenza, in subjects with RA.

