Potential Risk of Clinical Significance	Summary of Data/Rationale for Risk	Mitigation Strategy
		
inclusion in the study.
 
Withdrawal Criteria:
 
 
If a female subject should become pregnant during the study, study medication should be discontinued. The subject will be followed to determine the outcome of the pregnancy. Any pregnancy complication or elective termination of a pregnancy will be reported as an AE or SAE.
 

Drug Interaction	
Non-clinical data:
 
In vitro studies with GSK2982772 assessing potential drug-drug interactions with Cytochrome P450 3A4 (CYP3A4) substrates, P-glycoprotein (Pgp) inhibitors and OAT3 substrates were completed. To date, formal drug interaction studies in humans have not been performed with GSK2982772.
 
There is a low risk that GSK2982772 could be a perpetrator of OAT3 substrates. MTX is an OAT3 substrate in which GSK2982772 could potentially impair the clearance of MTX.
 
There is a low risk that GSK2982772 could be an inducer of CYP3A4 and therefore may lower circulating levels of concomitant medications that are metabolised by CYP3A4 when co administered with GSK2982772.
 
GSK2982772 is a Pgp substrate and therefore co administration with concomitant medications that are Pgp inhibitors could increase circulating levels of GSK2982772. See Section 4.3.6 of the GSK2982772 IB [GlaxoSmithKline Document 2014N204126_02].
	
Subject Selections:
 
 
Subjects who are taking concomitant medications known to inhibit Pgp or are CYP3A4 narrow therapeutic index (NTI) substrates will be excluded from the study. See Section 6.11.2 for a comprehensive list of medications.
 
 
Subject Monitoring:
 
 
Subjects' concomitant medication usage will be reviewed prior to inclusion and monitored throughout the study.
 
Subjects should be monitored throughout the study for potential effects of interaction between GSK2982772 and other concomitant medications.
 
PK sample collection to evaluate the potential interaction of GSK2982772 and MTX will be performed throughout the study.
 
Subjects should be monitored for potential effects of interaction between GSK2982772 and MTX.
 
Clinical laboratory results (e.g., liver function tests) are routinely being monitored throughout the study.
 

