#### 5.1. Inclusion Criteria

A subject will be eligible for inclusion in this study only if all of the following criteria apply:

AGE
1. Between 18 and 75 years of age inclusive, at the time of signing the informed consent.
TYPE OF SUBJECT AND DIAGNOSIS INCLUDING DISEASE SEVERITY
2. Subjects that do not have any medical conditions, other than moderate to severe RA that in the opinion of the Investigator put the subject at unacceptable risk or interfere with study assessments or integrity of the data. These medical conditions should be

stable at the time of screening and are expected to remain stable for the duration of the study.

3. Subject has had a confirmed diagnosis of rheumatoid arthritis according to the revised 2010 American College of Rheumatology/European League Against Rheumatism ACR-EULAR classification criteria.
4. Disease duration of  $\geq 12$  weeks (time from onset of patient-reported symptoms of either pain or stiffness or swelling in hands, feet or wrists) at screening.
5. Swollen joint count of  $\geq 4$  (28-joint count) and tender joint count  $\geq 4$  (28-joint count) at screening.
6. Subject has a DAS28 CRP disease activity score of  $\geq 3.2$  and CRP  $\geq 5.0$  mg/L ( $\geq 4.76$  nmol/L) at screening.
7. Subject must have received at least 12 weeks of non-biologic DMARD monotherapy or methotrexate (MTX)/DMARD combination therapy prior to screening AND must be on stable dose throughout the study.
8. Subject is naive to any biological therapies for RA

**OR**

Subject may have had previous exposure to a single anti-TNF biologic agent which was discontinued for reasons other than primary non-response more than 8 weeks (or 5 half lives whichever is longer) from first dose. **Note: Exposure to a single anti-TNF is not required in addition to Inclusion #7 above.**

9. For subjects who have consented to synovial joint biopsy:
  - a. Subject has an involved knee, wrist, or ankle suitable for biopsy, as assessed by a rheumatologist at screening.

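### Safety-driven reductions of background methotrexate or oral glucocorticoid are permitted in Table 1 and prohibited in Table 2, and the protocol does not settle whether such a subject is withdrawn

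*Protocol*

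**What the plan says.** Section 6.11.1, Table 1, sets the conditions for permitted background drugs. A subject on methotrexate must "remain on this dose throughout the study (unless dose must be reduced because of a safety concern"). NSAIDs and oral glucocorticoids must be stable "throughout the study (unless reduction required due to adverse effects").

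Section 6.11.2, Table 2, lists "A change in dose of methotrexate or other DMARD" as prohibited from 12 weeks before screening until after the follow-up visit. The next row prohibits oral prednisolone above 10 mg/day "or a change in dose of corticosteroid", from 4 weeks before screening until the same end point. Neither entry limits the direction of the change or the reason for it.

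Four other places bear on the point:
- Section 6.11.1 allows the Table 1 drugs under their stated requirements "and as long as they are not prohibited" in Section 6.11.2.
- Section 6.11.2 states the consequence: "Subjects who start prohibited medications or therapies as a treatment for RA or other reasons during the study will be withdrawn from study treatment".
- Section 5.4 treats withdrawal from study treatment as withdrawal from the study.
- Inclusion criterion 7 requires at least 12 weeks of DMARD therapy before screening "AND must be on stable dose throughout the study".

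**The concern.** A toxicity-driven reduction of background methotrexate or glucocorticoid is foreseeable in a 12-week trial of subjects with active disease. The protocol gives two instructions for it. An investigator working from Table 1 would make the reduction and keep the subject on study drug. One working from Table 2 would record a prohibited change and could withdraw the subject.

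The primary objective is safety, and methotrexate concentration is a secondary one. Section 4.6.1 says: "MTX is an OAT3 substrate in which GSK2982772 could potentially impair the clearance of MTX". If a reduction led to withdrawal at some sites, follow-up could end because of the interaction the trial is monitoring. At the least, whether the event counts as a protocol deviation would depend on which table the site had open.

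**Working it through.** No figure in the plan is at issue, so the check sets the provisions side by side and follows one event through them.

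**Step 1. Permitted or prohibited?**

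| Event during treatment | Table 1 | Table 2 | Result |
|---|---|---|---|
| Methotrexate reduced for safety | Allowed | Prohibited | Conflict |
| Oral glucocorticoid reduced for adverse effects | Allowed | Prohibited | Conflict |
| NSAID reduced for adverse effects | Allowed | No entry | No direct conflict |
| Sulfasalazine, (hydroxy)chloroquine or leflunomide dose changed | No exception | Prohibited | Consistent |

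The NSAID row would become a conflict only if the words on other DMARDs in Table 2 were read with the background in Section 2.2, which loosely counts NSAIDs among the synthetic DMARDs. That is too thin a basis for a finding.

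**Step 2. Does either table yield to the other?** Table 2 does not refer back to the Table 1 exceptions. It does print an exception where one is intended, in the row on prior exposure to a single anti-TNF agent, so silence in the methotrexate and corticosteroid rows is hard to read as an implied exception. The condition in Section 6.11.1 points towards Table 2 prevailing.

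**Step 3. Is the subject withdrawn?** Section 6.11.2 acts on subjects who *start* something prohibited. Section 5.4.1 is narrower: it speaks of initiating prohibited medication to treat RA. Lowering an existing drug is not literally a start. But Table 2 places the dose change itself in its column of therapies, and Section 6.11.2 covers therapies used for reasons other than RA. Withdrawal from treatment is therefore the likely reading, though not the only one. If it applies, Section 5.4 ends study participation as well.

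**Step 4. Does anything else resolve it?** Section 6.11.2 refers doubtful cases to the medical monitor, which is case-by-case advice. Section 7 allows waivers for immediate safety concerns, but does not say whether the subject then continues. The country-specific Amendment 4 repeats Table 1 and the withdrawal sentence; the text at hand stops before its Table 2, so that version cannot be checked further.

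**Step 5. Could the effect differ by arm?** The mechanism in Section 4.6.1 would act only in subjects taking methotrexate. Inclusion 7 does not require methotrexate, since other non-biologic DMARD monotherapy qualifies. Section 4.6.1 rates the interaction as low risk. The documents give neither the proportion on methotrexate nor an expected rate of dose reduction in either arm, so no size can be derived.

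**The case against.** The best defence is that a specific, reasoned exception in Table 1 would ordinarily be taken to qualify a general entry in Table 2. The condition in Section 6.11.1 can be read as applying to the drug, and methotrexate as such is not prohibited. Inclusion 7 is checked at screening, so it is weak as an on-study rule. And Section 6.11.2 speaks of starting a therapy, which a reduction is not. These arguments show that a lenient reading is available. They do not show that it is the only one, and none of them removes the dose change from the list of prohibited therapies.

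A reader might go further and infer that data would be lost selectively from the active arm, with a measurable loss of precision. The documents do not support this. Placebo subjects can also need a reduction, and the interaction is rated low risk. Any illustration needs an invented number of withdrawals. For instance, going from 16 to 14 or 12 active completers moves the zero-event upper limit in Table 5 from 19.5% to 21.8% or 24.7%. Those shifts overstate the loss: Table 5 counts completers, whereas the Safety Population in Section 9.3.1 keeps everyone who was dosed. The repeated-measures model in Section 9.4.2 uses visits before withdrawal, the Early Withdrawal visit collects the DAS28-CRP components, and Section 5.4 lets the sponsor replace withdrawn subjects.

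**Conclusion.** The contradiction is real for methotrexate and oral glucocorticoid: the same safety-driven reduction is allowed in one table and prohibited without exception in the other, and nothing in the text at hand reconciles them. Withdrawal from treatment, and so from the study, is the likely but not the certain consequence. The established harm is that sites may handle and classify the event differently. A relation to treatment arm is possible for methotrexate because of the interaction named in Section 4.6.1, but it is not established, and its size cannot be given from the documents. The conclusion rests on the wording of Sections 5.1, 5.4, 6.11.1 and 6.11.2 alone and assumes no event rate. It takes no position on which clinical rule is right.

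**What to change.** Reconcile Table 1, Table 2, Section 6.11.2 and Inclusion 7 so that one rule covers safety-driven reductions of background methotrexate and oral glucocorticoid. The choice of rule belongs to the clinical team. State explicitly whether the withdrawal provisions of Sections 6.11.2 and 5.4 apply to such a reduction, align Section 5.4.1 with the answer, and carry the wording into the country-specific version.

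Whichever rule is chosen, record the date, the old and new dose and the reason for each reduction, and report these events by arm. Section 6.7 already captures the date, time and weekly dose of methotrexate. For other concomitant drugs, Section 6.11.1 requires as a minimum only the name and dates, so dose and reason need to be added.

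The cost is protocol wording and a small addition to the case report form, with no extra subjects or visits. If the team also wants scheduled safety and DAS28-CRP assessments to continue after withdrawal from treatment, Section 5.4 must be reconciled too, because it now ends study participation at that point; those later visits would then be an added cost.

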## 7. STUDY ASSESSMENTS AND PROCEDURES

Protocol waivers or exemptions are not allowed with the exception of immediate safety concerns. Therefore, adherence to the study design requirements, including those specified in the Time and Events Table (Section 7.1), are essential and required for study conduct.

Supplementary study conduct information not mandated to be present in this protocol is provided in the SRM and laboratory manual. The SRM will provide the site personnel with administrative and detailed technical information that does not impact subject safety.

This section lists the procedures and parameters of each planned study assessment. The timing of each assessment is listed in the Time and Events Table Section 7.1

- At study visits, the Patient Reported Outcomes (PROs) should be completed prior to any other study assessments.
- The timing and number of planned study assessments, including safety, pharmacokinetic, pharmacodynamic/biomarker or others assessments may be altered during the course of the study based on newly available data (e.g., to obtain data closer to the time of peak concentrations) to ensure appropriate monitoring.
- The change in timing or addition of time points for any planned study assessments must be documented in a Note to File which is approved by the relevant GSK study team member and then archived in the study sponsor and site study files, but this will not constitute a protocol amendment.
- No more than 500 mL of blood will be collected over the duration of the study, including any extra assessments that may be required.
- The Institutional Review Board/Independent Ethics Committee (IRB/IEC) will be informed of any safety issues that require alteration of the safety monitoring scheme or amendment of the Informed Consent Form.

## 7.1. Time and Events Table

Procedures	Screening (-30)	Treatment Period 													Early Withdrawal 	Follow Up (±3) 
		Day 1	Day 8 (±3)	Day 15 (±3)	Day 22 (±3)	Day 29 (±3)	Day 36 (±3)	Day 43 (±3) (week 6)	Day 50 (±3)	Day 57 (±3)	Day 64 (±3)	Day 71 (±3)	Day 78 (±3)	Day 85 (+2) (week 12)		
Site Visit	X	X	X	X		X		X		X		X		X	X	X
Phone call					X		X		X		X		X			
General/Safety Assessments and Procedures																
Informed Consent	X															
Subject Demography	X															
Full medical history 	X															
Inclusion/Exclusion Criteria	X															
Full physical exam 	X													X	X	X
Brief physical exam		X 		X		X		X 		X		X				
Vital signs (BP, HR, RR, temperature)	X	X 	X	X		X		X 		X		X		X	X	X
12-lead ECG	X 	X 	X	X		X		X 		X		X		X	X	X
Concomitant medication review & AE reporting/SAEs 	X-----X															
PROs/Questionnaires/Diaries/Disease Assessments and Procedures																
Columbia Suicide Severity Rating Scale (C-SSRS)	X	X 						X 						X	X	
FACIT-fatigue; RA Symptom and Impact Diary 		X 						X 						X	X	
HAQ-DI; Patient Assessment of joint pain 		X 		X		X		X 		X		X		X	X	
Patient Global Assessment (PtGA) 	X	X 		X		X		X 		X		X		X	X	
Tender (28) & Swollen (28) joint count	X	X 		X		X		X 		X		X		X	X	
Physician Global Assessment (PGA)		X 		X		X		X 		X		X		X	X	
MRI/DCE-MRI 		X 						X 						X 	X 	

Procedures	Screening (-30)	Treatment Period 												Early Withdrawal 	Follow Up (±3) 	
		Day 1	Day 8 (±3)	Day 15 (±3)	Day 22 (±3)	Day 29 (±3)	Day 36 (±3)	Day 43 (±3) (week 6)	Day 50 (±3)	Day 57 (±3)	Day 64 (±3)	Day 71 (±3)	Day 78 (±3)			Day 85 (+2) (week 12)
Study Treatment																
Randomisation		X														
Study medication (three times daily) 		X	-----X													
Dispensing of study medication		X			X				X							
Dispensing of diary cards		X	X	X		X		X		X		X				
Collection and review of diary cards			X	X		X		X		X		X		X	X	
Laboratory (Safety) Assessments and Procedures																
TB, HIV, HepB, Hep C Ab, Anti-CCP, Anti-dsDNA, RF	X															
FSH & estradiol (if applicable)	X															
Serum pregnancy test (WCBP only)	X															
Urine pregnancy test (WCBP only) 		X 	X	X		X		X 		X		X		X	X	
Haematology, chemistry, urinalysis	X	X 	X	X		X 		X 		X 		X 		X	X	
CRP	X	X 		X		X		X 		X		X		X	X	
Blood sample for PD inflammatory biomarkers, mRNA, and TE 		X 						X 						X	X	
PK blood samples GSK2982772 		X	X 					X 						X	X	
PK blood samples for MTX 		X 	X 					X 								
Pharmacogenetic sample (PGx)		X 														
Synovial biopsies for PK, inflammatory biomarkers, mRNA, target engagement & pathway engagement analysis 		X 						X 							X 	

**Footnotes:**

1. Full medical history (includes past and current conditions, medication history, substance usage, and family history of premature CV disease).
2. Full physical exam (includes height/weight at screening, height not measured at later time points).
3. Triplicate ECG to be performed at screening only.
4. Pre-dose.
5. Any SAEs assessed as related to study participation (e.g., protocol-mandated procedures, invasive tests, or change in existing therapy) or related to a GSK product will be recorded from the time a subject consents to participate in the study up to and including any follow-up. AEs will be collected from the start of Study Treatment until the follow-up contact. On Days 22, 36, 50, 64, and 78, subjects will be questioned about their general health status via phone call.
6. All PRO assessments should be conducted on site before any tests, procedures, or assessments, to avoid influencing the subjects' perception.
7. DCE-MRI will be performed on all subjects, provided that sites have DCE-MRI capability and experience (e.g., hardware and software requirements). If sites do not have DCE-MRI capability or experience, a regular MRI will be performed of the affected hand/wrist. If the same joint is used for MRI and synovial biopsy, MRI should be performed before biopsy (if applicable).
8. Subjects must take study medication three times a day approximately 8 hours apart. Exact time of dosing to be recorded in diary cards. On Day 1, the first study dose will be administered at the site. On Days 8, 43 and 85 only, subjects must not take their medication at home in the morning. Subjects will complete pre-dose assessments and then will be administered their morning dose of medication at site on Days 8 and 43. On Day 85, subjects are no longer receiving study medication.
9. If urine pregnancy test is positive, a confirmatory serum pregnancy test must be performed.
10. Haematology and chemistry only. No urinalysis required on Days 29, 57 and 71. When clinical laboratory samples are taken on the same day as the MRI, the samples should be taken first prior to the administration of the contrast fluid with MRI. If this is not feasible (i.e. MRI is performed first), it is recommended that a separate IV catheter or straight venipuncture be performed in the *opposite* arm to where the MRI contrast fluid was administered.
11. Blood samples for inflammatory biomarkers, mRNA and target engagement. See laboratory manual for full details on sample collection, handling and shipment.
12. PK blood samples for GSK2982772 will be taken pre-dose on Days 8 and 43. Post-dose serial PK samples will be taken on Days 1, 8 and Day 43 at the following time points: 1, 2, 4, and 6 hours. A trough PK sample will be taken on Day 85 or at Early Withdrawal.
13. Only applicable if subjects are on MTX: PK blood samples for MTX will be taken pre-dose GSK2982772 on Day 1 (MTX alone), on Days 8 and 43 (MTX + GSK2982772). Subjects who are on MTX should ideally take their MTX dose on the same day of the week at approximately the same time of the day throughout the study. In addition, the Day 1, 8 and 43 visits should ideally be on the same day of the week.
14. A PGx blood sample is collected at the baseline visit, after the subject has been randomised and provided informed consent for genetic research. If the sample is not collected at the baseline visit, it can be collected at any time during the study after randomisation.
15. Synovial biopsies are optional.
16. Biopsy (if applicable) and MRI only are required at Early Withdrawal visit if subject withdraws after at least 14 days of treatment and prior to Day 43. If a subject withdraws between Days 43 and 57, an MRI is not required at the Early Withdrawal visit. If a subject withdraws on Day 57 or after, an MRI should be performed at the Early Withdrawal visit. A window allowance of  $\pm 3$  days of Early Withdrawal visit is allowed to perform the MRI.
17. Visit windows during the treatment period are relative to Day 1.
18. If a subject withdraws from the study, every effort will be made for the subject to complete an Early Withdrawal visit prior to the Follow Up visit.
19. Follow-up visit should be completed 28 days ( $\pm 3$  days) after the last dose of study medication.
20. MRI (and if applicable; a biopsy) may be performed during the screening window as an additional visit (if required) up to 7 days before Day 1 to allow sites flexibility in scheduling. The MRI must be completed prior to synovial biopsy (if performed on the same joint). The site should be reasonably confident that the subject has fully qualified for the study (e.g., screening clinical labs, vital signs, physical examination, etc.) before the MRI (and if applicable: a biopsy) is/are performed.

21. A biopsy (if applicable) and MRI may be performed on a separate day within the Day 43 window allowance ( $\pm 3$  days). A separate visit to perform the MRI followed by synovial biopsy (if applicable) is only allowed to accommodate scheduling. If biopsy is being performed, this visit must be scheduled after the Day 43 visit where the PK, clinical laboratory tests and other required Day 43 procedures are performed. Subjects must not take their study medication at home in the morning before the full Day 43 visit and also the morning before MRI and biopsy (if applicable) visit if being done on a separate day.
22. For MRI performed on day 85, a visit window of up to 2 days after is allowed in order to perform the MRI.

